1. LIST OF ABBREVIATIONS

α7nAChR α7 nicotinic acetylcholine receptor

 $A\beta_{42}$ amyloid beta₁₋₄₂

AChEI acetylcholinesterase inhibitor

AD Alzheimer's disease

ADAS-cog Alzheimer's Disease Assessment Scale – cognitive subscale

ADME absorption, distribution, metabolism, excretion

AE adverse event

ALT alanine transaminase
ALP alkaline phosphatase
ANOVA analysis of variance
AST aspartate transaminase
AUC area under the curve
BUN blood urea nitrogen

CFR Code of Federal Regulations
Cmax maximum plasma concentration
CRO contract research organization

CSF cerebrospinal fluid
CSI Cassava Sciences, Inc.
CT computed tomography
ECG electrocardiogram
CRF case report form

EDTA ethylenediaminetetraacetic acid FDA Federal Drug Association

FIH first in human FLNA filamin A

GCP good clinical practice
GLP good laboratory practice
HBsAg hepatitis B surface antigen

HCV hepatitis C virus

HED human equivalent dose

HIV human immunodeficiency virus hERG human ether-a-go-go-related gene

IB Investigator's Brochure ICF informed consent form

ICH International Council on Harmonization of Technical

Requirements for Registration of Pharmaceuticals for Human

Use

IR insulin receptor

IRB independent review board LOQ limit of quantitation

MMSE Mini Mental State Evaluation
NMDAR N-methyl D-aspartate receptor
NOAEL no observable adverse effect level

NOEL no observable effect level

PK pharmacokinetics

SavaDx blood-based diagnostic/biomarker candidate

RBC red blood cell

SAE serious adverse event

Simufilam small molecule drug candidate to treat AD

SOP standard operating procedure

Tmax time to Cmax

ULN upper limit of normal WBC white blood cell

2. INTRODUCTION

2.1. MECHANISM OF ACTION

Cassava Sciences, Inc. is developing simufilam, a novel drug candidate designed to treat and slow the progression of Alzheimer's disease (AD). Simufilam binds with femtomolar affinity to an altered conformation of filamin A (FLNA) that is induced by beta amyloid₁- $_{42}$ (A β_{42}), present in AD brain and critical to the toxicity of A β_{42} . Simufilam binding reverses the altered FLNA conformation and restores FLNA's native shape, preventing two toxic signaling cascades of $A\beta_{42}$. $A\beta_{42}$, in monomer or small oligomer form, hijacks the α 7-nicotinic acetylcholine receptor (α 7nAChR) and signals via this receptor to hyperphosphorylate tau. This signaling requires the recruitment of altered FLNA to this receptor. Second, altered FLNA also links to toll-like receptor 4 (TLR4) to allow Aβ₄₂ to persistently activate this receptor. Normal FLNA does not associate with either α7nAChR or TLR4. In addition to disrupting the normal functions of α7nAChR and tau protein, A_{β42}'s toxic signaling to hyperphosphorylate tau leads to the signature tangles and plagues in AD brain. In two AD mouse models and in postmortem human AD brain tissue, simufilam restored function of three receptors that are impaired in AD: the α7nAChR, the N-methyl-D-aspartate receptor (NMDAR), and the insulin receptor (IR).^{2,3} Simufilam also improved synaptic plasticity and reduced tau hyperphosphorylation, amyloid deposits, neurofibrillary tangles and inflammatory cytokine release.^{2,3} We therefore expect simufilam both to improve cognition and to slow AD progression. Both mouse models used a dose of 20 mg/kg/day (equivalent to 60 mg/m²/day).

2.2. SAFETY PHARMACOLOGY AND TOXICOLOGY

A robust nonclinical ADME, safety pharmacology, and general and genetic toxicology program has been conducted with simufilam. In vitro metabolic profiling showed minimal metabolism across several species including humans. Simufilam was rapidly absorbed and eliminated in in vivo studies in rat and dog with nearly 100% oral bioavailability, a 2.67-h half-life in dog, dose-proportional PK and no accumulation. Safety pharmacology studies showed no adverse effects on gross behavioral and physiological parameters in the Irwin test of CNS toxicity in rats, no adverse effects on respiratory rate, tidal volume or minute volume in the rat respiratory test, and no adverse effects on arterial blood pressure, heart rate and ECG parameters in the dog cardiovascular study. The in vitro hERG test for cardiotoxicity also indicated no adverse effect. A full battery of genotoxicity studies was conducted (in vitro bacterial Ames, in vitro chromosomal aberration, and in vivo rat micronucleus test) and were all negative. An in vitro specificity screen showed no significant activation or inhibition of a panel of 68 receptors, channels and transporters.

Simufilam was tested in repeat dose oral toxicity studies in rats and dogs. A 6-month repeat dose oral toxicity study in rat (PTI-125-NC-049) used the same doses as a 28-day study (50, 500 and 1000 mg/kg/day), which found 500 mg/kg/day to be the no observable adverse effect level (NOAEL). In the 6-month study, the toxicological response was characterized by decreased body weights and adverse structural and functional alterations in the liver of 500 and 1000 mg/kg animals, including increased weight, hepatocellular hypertrophy and vacuolation, single/multiple basophilic/ eosinophilic/clear cell focus, hepatocellular degeneration, pigmentation, and oval cell hyperplasia. The presence of bile pigment was consistent with cholestasis. These findings correlated with changes to the clinical chemistry profile, including increased ALP and total/direct bilirubin. Over the 1-month recovery period, there was complete recovery of the hepatocellular degeneration and partial recovery of hepatocellular hypertrophy. The NOAEL from this 6-month study was 50 mg/kg/day (equivalent to 300 mg/m²). A second 6-month repeat dose oral toxicity study in rat, pending pathology, will more accurately determine the 6-month NOAEL in rat. Doses are vehicle and 125 and 250 mg/kg/day.

In a 9-month toxicity study in dog (PTI-125-NC-050), the no observable effect level (NOEL) of simufilam was 25 mg/kg. The 200 mg/kg (high) dose was decreased to 150 at 1 month due to bodyweight loss thought unsustainable for 9 months. Clinical signs were salivation and a few instances of muscle fasciculations. There were no pathology findings, but the high dose was considered adverse due to two unexplained deaths. The 75 mg/kg/day NOAEL provides 38- and 19-fold safety margins by C_{max} and AUC, respectively, over the 100 mg b.i.d. dose in patients.

2.3. CLINICAL STUDIES

A first-in-human, double-blind, Single Ascending Dose clinical trial was conducted in healthy normal volunteers, age 18-45 with oral dosing solution. Doses were placebo, 50, 100 and 200 mg (equivalent to 31, 62, and 123 mg/m², respectively) administered to three different groups of volunteers. The study showed dose proportional PK, and there were no drug-related adverse events (AEs).

In a Phase 2a 28-day study, 13 mild-to-moderate AD patients received simufilam 100 mg b.i.d. as oral tablets. Patients were MMSE \geq 16 and \leq 24, age 50-85, with a CSF total tau/A β 42 ratio \geq 0.30. A second CSF sample was collected on Day 28, allowing assessment of change from baseline in biomarkers using commercial ELISA kits. All 8 biomarkers that are elevated in AD were significantly reduced from baseline (**Fig. 1**).⁴ A β 42, which is low in AD, was increased slightly but non-significantly. Reduced inflammatory cytokines and YKL-40 indicated reduced neuroinflammation. A reduced neurodegenerative drive was suggested by reductions in neurogranin, neurofilament light chain, and total tau. The robust reduction in phospho-tau (P-Tau181) confirms the mechanism of action of simufilam. Simufilam was safe and well tolerated in all patients.

Fig. 1 Mean Change from Baseline to Day 28 in CSF biomarkers (±SEM)

Pharmacokinetic analysis indicated minimal accumulation (ratio 1.36, based on overall exposure) and consistent clearance and apparent volume of distribution across study days. Steady state concentration was achieved by Day 7 and were maintained through Day 28.

A Phase 2b randomized clinical trial of simufilam 50 or 100 mg tablets or placebo (1:1:1) enrolled 64 mild-to-moderate AD patients. Both doses significantly improved eleven CSF biomarkers of AD pathology, neurodegeneration, neuroinflammation and blood-brain barrier integrity (**Fig. 2**). CSF biomarker analyses were conducted blind to treatment and timepoint by an outside lab. These data suggest disease modification and replicate the Phase 2a results in a well-controlled study.

[figure not shown]

Fig. 2 Phase 2b Mean Change from Baseline to Day 28 in CSF biomarkers (±SEM)

The secondary endpoints in the Phase 2b trial were two cognitive measures using the Cambridge Neuropsychological Test Automated Battery. Patients were assessed on the Paired Associate Learning (PAL) test, measuring episodic memory, and a test of spatial working memory. The primary outcome measures for each were total errors, with errors imputed for more difficult levels not reached in the PAL test. Simufilam produced encouraging effect sizes (calculated by Hedge's g for group sizes of 20), suggesting cognitive enhancement (**Fig. 3**). Effect sizes versus placebo for the test of episodic memory were 37% and 23% for the 50 and 100 mg groups, respectively, after removing the most and least impaired subjects by baseline score. For spatial working memory, effect sizes were 17% and 46% for these respective dose groups. Cognitive enhancement by simufilam is supported by preclinical data showing improved function of α 7nAChR, NMDAR and insulin receptors and improved synaptic plasticity in 3xTg AD mice and in postmortem human AD brain tissue. In both Phase 2 clinical trials, simufilam was well tolerated and no patients discontinued due to AEs.

[figure not shown]

Fig. 3 Phase 2b Mean Change from Baseline to Day 28 in Total Errors in Memory Test

To benefit participants of previous one-month studies and to assess longer-term clinical safety of simufilam, a 1-year, open-label clinical trial of approximately 100 mild-to-moderate AD patients is ongoing. All prior patients were eligible, and new patients (MMSE 16-26) can enroll. All new patients have a baseline CSF draw, and change in biomarkers will be evaluated after 6 or 12 months. Additionally, cognition is being assessed with the ADAS-Cog and neuropsychiatric symptoms by the NPI.

3. STUDY OBJECTIVES

The objectives of this study are 1) to assess the effect of food on the rate and extent of absorption of simufilam, and 2) to compare the pharmacokinetic profile of the Phase 3 formulation of simufilam to that of the earlier Phase 2 formulation. The new Phase 3 formulation has a higher percentage of active ingredient and is therefore smaller with a slightly different shape.

4. SUMMARY OF STUDY DESIGN

This is a single-center, randomized, four-treatment, four-sequence crossover study in healthy volunteers to estimate the effect of food on the PK of simufilam following oral dosing of the Phase 3 simufilam 100 mg tablet. Additionally, the relative bioavailability of the Phase 3 tablet will be compared to the earlier Phase 2 simufilam 100 mg tablet, both in the fasted state. A total of twenty four (24) healthy volunteers (12 male and 12 female) will be enrolled into this study. Subjects will be randomly assigned to one of four treatment sequences (6 subjects/sequence) as shown in **Table 6**.

Table 6 Treatment Sequence

	Treatment Period 1			Treatment Period 2			Treatment Period 3				Treatment Period 4					
Sequence	Fasted	High	Low	Phase 2 Tablet	Fasted	High	Low	Phase 2 Tablet	Fasted	High	Low	Phase 2 Tablet	Fasted	High	Low	Phase 2 Tablet
Sequence A (n = 6)				X			X		X					X		
Sequence B (n = 6)	X							X		X					X	
Sequence C (n = 6)		X			X						X					X
Sequence D (n = 6)			X			X						X	X			

During each 48-h treatment period, subjects will be given a single oral dose of simufilam as displayed in **Table 6**. The administration of each dose of study drug will be separated by a 48-hour washout period. PK blood samples will be obtained prior to dosing and at specified intervals during the study (0-48 h post-dose for Treatment Periods 1 - 4). The observation period for safety will continue through the incarceration period.

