After dosing, the following assessments will be conducted:

- Vital signs (blood pressure, pulse and respiration rate) at approximately 30 and 90 min, and 4, 8, 12, h post-dose (within 15 min of nominal time)
- Blood samples will be drawn at 20, 40, and 60 min and at 1.5, 2, 2.5, 3, 4, 6, 8, 10, 12 and 24 h after dosing for PK assessments (as close as possible to nominal time, but within 5 min for timepoints up to 3 h and within 15 min thereafter).
- Adverse event monitoring

All subjects will receive a meal 4 h post-dose. All meals for the first 24 h after dosing will be served at a fixed time interval after dose administration, such that meals are served in a staggered fashion.

6.5.4. Washout Periods – Days 2, 4 and 6

The following assessments will be conducted:

- Blood sample collection for PK prior to breakfast
- Vital signs (blood pressure, temperature, pulse and respiratory rate) at approximately 4 and 12 h after the PK sample collection
- Adverse event monitoring

6.5.5. Treatment Periods 2, 3 and 4 – Days 3, 5 and 7

According to each subject's sequence assignment, subjects to receive the first dose **fasted** will fast for at least 10 h prior to dosing. Water will be allowed until 1 h before dosing.

On the morning of Study Days 3, 5, and 7, prior to dosing, subjects to be administered simufilam in a **fed** state will consume either a **high-fat** or **low-fat** breakfast, according to their sequence assignment and as described in the Section 6.2 above. The simufilam tablet will be administered 30 min after the start of the meal.

The following will be conducted in the morning of Study Days 3, 5, and 7:

- Vital signs, within 1 h before dosing (blood pressure, pulse, temperature and respiration rate)
- Blood sample collection for PK assessment, within 1 h before dosing (Time = 0)

The simufilam tablet will be administered with 240 mL of water, **30 min after the start of the meal** (if dosing in a fed state). No additional water will be allowed until 1 h post-dose. No food will be allowed until 4 h post-dose.

After dosing, the following assessments will be conducted:

- Vital signs (blood pressure, pulse and respiration rate) at approximately 30 and 90 min, and 4, 8, 12, h post-dose (within 15 min of nominal time)

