- Blood samples will be drawn at 20, 40, and 60 min and at 1.5, 2, 2.5, 3, 4, 6, 8, 10, 12 and 24 h after dosing for PK assessments (as close as possible to nominal time, but within 5 min for timepoints up to 3 h and within 15 min thereafter).
- Adverse event monitoring

All subjects will receive a meal 4 h post-dose. All meals for the first 24 h after dosing will be served at a fixed time interval after dose administration, such that meals are served in a staggered fashion.

6.5.6. Day 8

The following tests will be performed at Day 8 before discharge:

- Blood sample collection for PK prior to breakfast
- Blood draw for clinical laboratory tests, chemistry hematology and urine sample for urinalysis
- Vital signs (blood pressure, temperature, pulse and respiratory rate)
- Physical examination, excluding height, weight and BMI
- A 12-lead ECG
- Adverse event monitoring

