## 5 RANDOMIZATION

QMD Ref: Worldwide-TMP-ST-006-4.0 Effective: 12Aug2019	Governing QMD: Worldwide-SOP-ST-001
Confidentiality Statement	

This document is the property of Worldwide Clinical Trials Inc. and may not be duplicated, copied, altered or removed from company without prior approval from Worldwide Quality Assurance or in compliance with Worldwide Standard Operating Procedures.

Worldwide Clinical Trials Controlled Quality Management Document									
 WORLDWIDE CLINICAL TRIALS					Sponsor:		Cassava Sciences, Inc		
					Protocol Number:		PTI-125-05		
STATISTICAL ANALYSIS PLAN – PHASE 1									

Subjects will be randomly assigned to one of four treatment sequences (6 subjects/sequence) to receive a single oral dose of simuflam in each treatment period either under fasted condition or low fat fed condition or high fat fed condition or phase 2 tablet as shown in Table 1.

The administration of each dose of study drug will be separated by a 48-hour washout period. PK blood samples will be obtained prior to dosing and at specified intervals during the study (0-48 h post-dose for Treatment Periods 1 - 4). The observation period for safety will continue through the incarceration period.

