### 6.2.1 Treatment Period / Visits

Each visit as per study schedule will be mapped to treatment period and analysis visit for summary tables as given below. Listings will reflect actual period and visit as defined in protocol.

Collected visit	Treatment Period	Analysis visit
Screening	-	Screening
DAY 0 Check-in	-	Check-in
DAY 1	Period 1	Day 1
DAY 2	Period 1	Day 2
DAY 3	Period 2	Day 3
DAY 4	Period 2	Day 4
DAY 5	Period 3	Day 5
DAY 6	Period 3	Day 6
DAY 7	Period 4	Day 7
DAY 8	Period 4	EOS / ET
Early Termination	Subject's last treatment period	EOS / ET

QMD Ref: Worldwide-TMP-ST-006-4.0 Effective: 12Aug2019	Governing QMD: Worldwide-SOP-ST-001
Confidentiality Statement	

This document is the property of Worldwide Clinical Trials Inc. and may not be duplicated, copied, altered or removed from company without prior approval from Worldwide Quality Assurance or in compliance with Worldwide Standard Operating Procedures.

Worldwide Clinical Trials Controlled Quality Management Document			
 WORLDWIDE CLINICAL TRIALS	Sponsor:	Cassava Sciences, Inc	
	Protocol Number:	PTI-125-05	
STATISTICAL ANALYSIS PLAN – PHASE 1			

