### 6.2.10 PK Parameters

Concentration-time data for simufilam will be analyzed using noncompartmental methods in Phoenix™ WinNonlin® (Version 8.1 or higher, Certara, L.P.) in conjunction with the internet-accessible implementation of Pharsight® Knowledgebase Server™ (PKSO; Version 4.0.4, Certara, L.P.). Concentrations that are below the limit of quantification (BLQ) will be treated as zero in the data summarization and descriptive statistics.

QMD Ref: Worldwide-TMP-ST-006-4.0 Effective: 12Aug2019	Governing QMD: Worldwide-SOP-ST-001
Confidentiality Statement	

This document is the property of Worldwide Clinical Trials Inc. and may not be duplicated, copied, altered or removed from company without prior approval from Worldwide Quality Assurance or in compliance with Worldwide Standard Operating Procedures.

Worldwide Clinical Trials Controlled Quality Management Document			
 WORLDWIDE CLINICAL TRIALS	Sponsor:	Cassava Sciences, Inc	
	Protocol Number:	PTI-125-05	
STATISTICAL ANALYSIS PLAN – PHASE 1			

Blood samples for PK samples for the determination of simufilam will be collected at pre-dose (0), and at 0.333 (20 min), 0.667 (40 min), 1, 1.5, 2, 2.5, 3, 4, 6, 8, 10, 12, and 24 hours post-dose, for each treatment period.

Mean plasma concentration-time data will be presented graphically on both linear and semi-log scales using nominal time. Spaghetti plots and individual plots will be presented on both linear and semi-log scales using actual time. The following plots will be created:

- 1) Mean plot: Phase 3 Simufilam Tablet Fasted, Low-fat, and High-fat
- 2) Mean plot: Phase 2 Simufilam Tablet Fasted, Phase 3 Simufilam Fasted
- 3) All Subject plot: All subjects in one plot per Treatment
- 4) Individual Subject plot: Phase 3 Simufilam Tablet Fasted, Low-fat, and High-fat plotted together for each subject
- 5) Individual Subject plot: Phase 2 Simufilam Tablet Fasted, Phase 3 Simufilam Fasted plotted together for each subject

Individual plasma concentrations from subjects that were excluded from the PK Analysis Population will be listed in Concentration Listings.

Concentration-time data for simufilam in plasma will be analyzed using non-compartmental methods. The following descriptive statistics will be presented by treatment and nominal time: sample size (N), arithmetic mean, standard deviation (SD), coefficient of variation (CV%), minimum, median, and maximum.

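### Does the 0-48 h sampling window in Protocol 4 and SAP 5, against sampling lists that stop at 24 h, leave the PK analysis undefined?

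*Protocol*

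**What the plan says.** Two descriptive passages give a 48-h window. Protocol 4 says PK samples are taken "at specified intervals during the study (0-48 h post-dose for Treatment Periods 1 - 4"), and SAP 5 repeats "0-48 h post-dose for Treatment Periods 1 - 4". Protocol 4 also describes the period itself as 48 h long: "During each 48-h treatment period, subjects will be given a single oral dose of simufilam".

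The passages that list the samples stop at 24 h:

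- Protocol 6.5.3 (Period 1) and 6.5.5 (Periods 2 to 4) both end with "1.5, 2, 2.5, 3, 4, 6, 8, 10, 12 and 24 h after dosing for PK assessments".
- SAP 6.2.10 ends its list with "6, 8, 10, 12, and 24 hours post-dose, for each treatment period".
- Protocol 6.5.5 gives Days 3, 5 and 7 a further draw: "Blood sample collection for PK assessment, within 1 h before dosing (Time = 0").
- Protocol 6.5.6 places the last PK draw on Day 8: "The following tests will be performed at Day 8 before discharge".

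On which day belongs to which period, SAP 6.2.1 states: "Each visit as per study schedule will be mapped to treatment period and analysis visit for summary tables as given below". Its table puts Days 3, 5 and 7 in Periods 2, 3 and 4, and Day 8 in Period 4 as end of study.

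**The concern.** AUClast is listed as a primary endpoint in SAP 3.1, and it depends on where the last quantifiable sample lies. The same SAP carries both windows: 48 h in section 5 and 24 h in section 6.2.10.

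The worry becomes sharper because blood is drawn about 47 to 48 h after the previous dose in Periods 1 to 3, just before the next dose. Someone working from the design summary could append that value to the previous profile. Period 4 has no such draw, so three periods would have a 48-h profile and one a 24-h profile. AUClast would then be cut off differently by period, and one might fear that the food-effect and formulation ratios would be distorted.

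**Working it through.** **1. Can the 48-h window be met?** The doses are on Days 1, 3, 5 and 7 (Protocol 6.2). The lists hold 14 times including pre-dose, the last at 24 h.

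| Period | Dose | 24-h sample | 48 h falls on | Draw near 48 h |
|---|---|---|---|---|
| 1 | Day 1 | Day 2 | Day 3 | pre-dose of Period 2, 47-48 h |
| 2 | Day 3 | Day 4 | Day 5 | pre-dose of Period 3, 47-48 h |
| 3 | Day 5 | Day 6 | Day 7 | pre-dose of Period 4, 47-48 h |
| 4 | Day 7 | Day 8 | Day 9 | none; discharge is on Day 8 |

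So 48 h is not a listed post-dose time in any period, and it cannot be reached in Period 4. In Periods 1 to 3 the phrase is a loose but arguable description of when blood is drawn.

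**2. What does the analysis text instruct?** SAP 6.2.10 names the times for each period and computes AUClast to the last quantifiable concentration, using actual time relative to dosing. Protocol 6.5.5 labels the Day 3, 5 and 7 pre-dose draw as time zero, and SAP 6.2.1 places those days in the new period. No passage assigns the draw to the earlier profile. The result is one 24-h profile per period, with no numerical effect.

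**3. What if an analyst departed from that text?** Take the pre-dose draws as 48-h points in Periods 1 to 3.

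Assumptions:

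- One compartment, C(t) proportional to ka/(ka - k) x (exp(-kt) - exp(-ka t)), with ka from 1.5 down to 0.5 per h.
- A quantifiable 48-h value. The assay limit is not in the documents.
- Half-lives of 2.67 h (dog, Protocol 2.2), 4 h and 8 h (assumed), and one inferred from the accumulation ratio of 1.36 in Protocol 2.3. For a 12-h interval, k = -ln(1 - 1/1.36)/12 = 0.1108 per h, so t1/2 = ln 2/0.1108 = 6.26 h.

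The extra linear trapezoid is 24 x (C24 + C48)/2. Each treatment has 18 of its 24 profiles in Periods 1 to 3, so its geometric mean rises by the individual ratio to the power 0.75. The last column fits subject, period and treatment terms to the Table 6 sequences, with ka 0.5 for high-fat and 1.5 for the other treatments. It compares the mixed window with 24 h throughout.

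| t1/2 (h) | AUClast with/without 48-h point | C48/Cmax | Geometric mean by treatment | High-fat/Fasted, mixed vs all 24 h |
|---|---|---|---|---|
| 2.67 | 1.007-1.012 | 0.0007-0.0016% | +0.5 to 0.9% | 1.0037 |
| 4 | 1.036-1.049 | 0.04-0.07% | +2.7 to 3.7% | 1.0092 |
| 6.26 | 1.113-1.136 | 0.7-1.0% | +8 to 10% | 1.0155 |
| 8 | 1.175-1.203 | 2.0-2.7% | +13 to 15% | 1.0181 |

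With the same ka for every treatment, all ratios stay at 1.0000. A common gain adds the same constant on the log scale to every Period 1 to 3 observation, and the period effect in SAP 6.10 absorbs it. Against 48 h throughout, High-fat/Fasted moves by -0.1% to -0.6%.

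**4. Does stopping at 24 h hurt AUCinf?** Under mono-exponential decline the share beyond 24 h is exp(-24k): 7.0% at 6.26 h and 12.5% at 8 h. Both are below the 30% extrapolation limit in SAP 6.2.10.

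**The case for a change.** The best case for acting is that the text is wrong as it stands, in two current documents, and that Period 4 removes any charitable reading, since the phrase explicitly covers Periods 1 to 4. The SAP holds both windows and declares no change from the protocol analysis. A report author copying the design summary would describe sampling that the trial does not do. The correction would cost a few words.

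What stands is the contradiction, together with the impossibility of a 48-h sample in Period 4. What does not stand is the step from there to the analysis. The 48-h phrase sits in a design overview and in the SAP's Randomization section, and neither instructs anyone how to compute a parameter. The mapping in SAP 6.2.1 is written for summary tables, so on its own it would be weak support. The time-zero label in the Protocol and the explicit list in SAP 6.2.10 do not share that limit.

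The larger percentages in the table arise only if someone sets the list aside and the 48-h value is quantifiable. At a 2.67-h half-life the assay would have to read 0.0007 to 0.0016% of Cmax. A terminal value below the limit is treated as missing under SAP 6.2.10 and adds nothing.

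**Conclusion.** This is a clerical slip: a summary phrase in Protocol 4 and SAP 5 that does not match the sampling lists or the Day 8 discharge. The detailed sections already fix the sampling times, the role of the pre-dose draw and the end point of AUClast, so an analyst who follows them gets a uniform 24-h profile in every period. The effect on planned estimates and treatment ratios is nil.

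Even under a misreading that the plan does not support, ratios would be unchanged for a common gain and would move by at most 1.8% in the unequal-absorption case. That bound rests on assumed absorption rates, on half-lives up to 8 h and on a quantifiable 48-h value; the documents state no human half-life. The descriptive means by treatment would move more, by up to 15%, under the same conditions.

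Aligning the phrase would be an editorial tidy-up with no gain for any result or conclusion, so no change to the plan follows.
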